- **2.3 Reducing dementia-screening bias for people with low health literacy.** Dementia screening tools are confounded with health literacy, but no means exist for correcting this test bias. Moreover, dementia-screening tools have not been validated for use by patients with low health literacy. Thus, screening may be inaccurate, leading to over-and under-diagnosis and in turn wasted resources on inappropriate care. A false-positive diagnosis is also extremely distressing for the patient. Thus, improvements in dementia screening are needed. Our goal is to determine differences in psychometric properties of dementia screening tools that are widely used in the clinical setting.

3.0 Inclusion and exclusion criteria:

In-person protocol:

Inclusion criteria:

- 1) Be 18 years of age or older
- 2) Be willing to provide informed consent, including signing the consent form
- 3) Be willing to be randomized to administration method
- 4) Be willing to complete questionnaires and interviews
- 5) Be fluent in English and/or Spanish
- 6) Be willing to attend three face-to-face sessions
- 7) Have no plans to move out of the study area in the next six months

Exclusion criteria:

- 1) Significant cognitive or neurologic impairment
- 2) Being a prisoner, detainee, or in police custody
- 3) Unable to complete the consent process
- 4) Inadequate vision to see study materials (worse than 20/80 corrected)
- 5) Inadequate hearing or manual dexterity to use the computer system

Phone-based protocol:

Inclusion criteria:

- 1. Enrollment in the in-person protocol (including all inclusion/exclusion criteria from in-person protocol)
- 2. Access to reliable phone connection
- 3. Be willing to participant in three phone-based sessions

Exclusion criteria:

- 1. Unable to complete the consent process
- 2. Inadequate hearing for phone-based assessments

4.0 Procedures Involved:

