- 4.14Cognitive impaired adults. Participants with severe cognitive impairment will be considered ineligible for this study. The research coordinator will administer a cognition screener (i.e., SPMSQ) that assess for any severe cognitive impairment to determine eligibility for this study. Participants with known mild-to-moderate cognitive impairment may be referred by clinicians to enhance our participant sample for the dementia supplement. Only those deemed capable of providing consent (based on the SPMSQ score) will be considered for the study and their diagnosis of mild-to-moderate cognitive impairment will be noted in the study's REDCap project.

5.0 Multiple sites:

- 5.1 Study sites. This study is being conducted at two sites: Northwestern University and Boston University Medical Center (BUMC). [name] is the PI of the Northwestern site and [name] is the PI of the BUMC site. Northwestern is the grant-holding site with [name] as the contact PI, but both PIs share overall leadership of the study. Both sites will recruit an equal number of participants (N = 608).
- 5.2 Required approvals. Recruitment will proceed at each individual site only when approved by the local IRB.
- 5.3 Site coordination. The sites are in frequency phone and email contact, and there is a weekly teleconference in place for the PIs and research coordinator to aid in consistency of study procedures. An all-team meeting is scheduled for once per month. To ensure that both sites are using the appropriate documents for the study, there is a shared, secure site on Box.com for all study materials (Note: No patient data or PHI is stored on Box, only study materials). Modifications to study protocols will be discussed among the team during the weekly teleconferences. These teleconferences will also be used to discuss problems, interim results, and eventual closure of the study.
- 5.4 Data management and security. The entire study team has been briefed on proper data management and security procedures. This includes the maintenance of data only on secure study trackers, managed via REDCap. Data security will be a weekly agenda item and data security will be routinely audited in terms of physical records (i.e., paper questionnaires and consent forms) as well as study files. Any and all non-compliance with the study protocol or applicable requirements will be reported to the appropriate IRBs in accordance with local policy.

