To enhance the study's sample of older adults and adults with mild-to-moderate cognitive impairment, the research team will collaborate with physicians that see these patients for recruitment into the study. The research team has requested access from the Mesulam Center for Cognitive Neurology and Alzheimer's Disease Center (CNADC) to use their registry of adults with mild-to-moderate cognitive impairment. We will also partner with other collaborators within NMHC, such as neuropsychologists, gerontologists, etc. to see if they would be interested in referring their patients to our study. The research team has also partnered with a [name] who is a member of the advisory board at the Woodson Regional Library, Chicago's first Dementia-friendly library in the Washington Heights neighborhood of Chicago. [name] has agreed to provide recruitment support from members in the community he serves at Woodson Regional Library and via the Endeleo Institute.

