We hypothesize that DIF will be observed across adequate versus low levels of health literacy as measured by HealthLiTT.¹⁵ This hypothesis was formulated before any data were examined. In terms of direction, we predict that low-health-literacy groups will show lower item slopes. All questionnaires and subscales mentioned in the “Core battery for DIF Testing” section of protocol will undergo DIF testing. To examine DIF across health literacy status, we will conduct separate analyses within language and within testing format (paper-based vs. talking touchscreen). The overall N for these analyses, within strata, will be 304. We will use the *lordif* package in R for these analyses. This involves several steps. Four models are fit to the data (see Box 1). The models are regressions that link the probability of response type (e.g., “never”, “rarely”, “sometimes”, “often”, “always”) to a latent trait. If an item is free of DIF, then group (e.g., adequate vs. low health literacy) should have no effect. Thus, Model 2 and Model 3 should not fit significantly better than Model 1. It is well known that statistical significance is influenced, in part, by sample size. Thus, *lordif* uses effect-size measures to detect DIF, and to flag individual items where the effect of group exceeds a particular threshold. Effect sizes indicative of DIF will be chosen for each scale based on a Monte Carlo simulation carried out in *lordif*, which returns an effect size that would be unlikely given the null hypothesis of no DIF.

The following *a priori* decisions are important. We will use a Type I error rate of $\alpha = .01$ to generate the McFadden ΔR^2 effect size for each item that would be considered unusual if the null hypothesis of no DIF were true. Within each scale, we will select the smallest McFadden R^2 across all of the items. The minimum effect size we will consider

Box 1: Models fit by lordif

Model 0: $\text{logit}[P(Y \geq k)] = \alpha_k$
Model 1: $\text{logit}[P(Y \geq k)] = \alpha_k + \beta_1 (\text{ability})$
Model 2: $\text{logit}[P(Y \geq k)] = \alpha_k + \beta_1 (\text{ability}) + \beta_2 (\text{group})$
Model 3: $\text{logit}[P(Y \geq k)] = \alpha_k + \beta_1 (\text{ability}) + \beta_2 (\text{group}) + \beta_3 (\text{ability} \times \text{group})$

Note: α and β are logistic regression parameters. k refers to the number of thresholds needed for each item.

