Differential Item Functioning of Depression by Cognitive Ability (MoCA-B)

With funding from a National Institute on Aging (NIA) Supplement, we have collected data on the Montreal Cognitive Assessment Test – Basic (MoCA-B). Data from the current project provide an opportunity for preliminary data for an upcoming grant proposal on the relationship between cognitive function and health-related quality of life. Thus, we will conduct DIF analyses of the depression scale of the PROMIS Profile and the PHQ-9 using high vs. low scorers on the MoCA-B as determined by a median split. The procedures of the DIF analyses will be the same as described above. We will also conduct visual analysis of the relationship between the MoCA-B and depression using the *ggplot2* package of R, as well as quantify the associations among these scales using Pearson correlations along with 95% CIs.

These analyses will be interim, before all data have been collected, as they will be needed for a grant submission in June of 2020. The results of this interim analysis will not affect any planned hypotheses presented elsewhere in this plan. The data analyzed for this interim analysis will be all data collected before 01 March 2020.

Health Literacy as a Possible Mediator Between Demographics and Symptoms Related to Stress and Trauma: An Application Of The Paasche-Orlow & Wolf Model

Added 02 October 2024 for Version 5.1

Health literacy has been highlighted as a barrier to service utilization and thus significantly impacts disease outcomes⁶². Outcomes may be impacted by an individual's difficulty with proper medication dosage or lack of trust in the healthcare system, as examples^{63, 64}. Both physical and mental health outcomes are important, including mental health symptoms related to stress and trauma, which people with low health literacy may experience at a high frequency. Although health literacy can be linked to mental health conditions such as depression, less is known about its connection to trauma-related symptoms. To address this gap, this study will identify the impact of health literacy on trauma-related symptoms as measured by the PCL-5. We will also explore the association between the PCL-5 and health-related quality of life measured by the PROMIS Profile.

Aims:

1. Determine the association between health literacy and symptoms related to stress and trauma measured by the PCL-5 scale, while controlling for demographic variables. Language can be explored as a moderator.

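### No literacy analysis uses the recorded diagnosis of cognitive impairment, so DIF due to impairment could be attributed to health literacy; the size is unknown

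*Protocol*

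**What the plan says.** **Entry into the sample.** Protocol 4.14 says: "Participants with known mild-to-moderate cognitive impairment may be referred by clinicians to enhance our participant sample for the dementia supplement". The Recruitment section adds: "To enhance the study's sample of older adults and adults with mild-to-moderate cognitive impairment, the research team will collaborate with physicians". It also mentions a requested registry of people with impairment. No separate cohort is described. SAP Table 2 is built on site, language, literacy, sex, mode and order, with no cell for referrals.

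**Flag.** Protocol 4.14 and 8.0 say that "their diagnosis of mild-to-moderate cognitive impairment will be noted in the study's REDCap project".

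**Exclusion wording.** Protocol 3.0 lists "Significant cognitive or neurologic impairment" as an exclusion, and the SAP's Data Collection Procedures section repeats the word *significant*. Protocol 4.14 and 8.0 exclude only *severe* impairment on the SPMSQ and allow mild-to-moderate impairment.

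**Literacy analyses.**
- Primary DIF compares Health LiTT T scores below 55 with 55 and above, within language and testing format. Box 1 contains only ability, group and their product. On direction, the SAP says "we predict that low-health-literacy groups will show lower item slopes".
- The MNLFA slope equation contains Health LiTT, administration type and their interaction.
- The depression moderation models contain symptom scales and Health LiTT, and no cognition term.

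**Cognition as a DIF source.** Under other interim and exploratory analyses, the SAP says "we will conduct DIF analyses of the depression scale of the PROMIS Profile and the PHQ-9 using high vs. low scorers on the MoCA-B", cut at the median. Literacy is not in that analysis, and its results are declared to have no bearing on hypotheses elsewhere in the plan.

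**The concern.** Literacy groups are observed, not randomised, so any characteristic that is more common in one group can produce DIF between them. Here the plan itself allows recruitment of people with one such characteristic, for a purpose other than the literacy question.

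The sponsor already sees the overlap. Protocol 2.3 says: "Dementia screening tools are confounded with health literacy, but no means exist for correcting this test bias". The protocol describes its health literacy measures as performance-based (4.6), so impairment may itself lower Health LiTT and move people below 55. That is an inference, not something the documents state.

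At stake is the attribution. The primary conclusion is meant to be that certain items work differently because of health literacy. If part of that difference comes from diagnosed impairment, the item list would not carry over to people who only have low literacy. The randomised comparison of paper with touchscreen is less exposed, since impairment should be balanced across modes in expectation.

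**Working it through.** **Step 1: the plan's own figure.** Table 2 has 16 cells of 76, so 16 × 76 = 1216. Over two languages and two modes, 1216 / 4 = 304, the SAP's stated N per stratum, or 152 per literacy group if split evenly. The final N of 728 gives a mean of 728 / 4 = 182 per stratum, or 91 per group.

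**Step 2: could MoCA-B adjustment replace the flag?** The SAP counts 478 participants with cognitive measures. 478 / 728 = 66%, so about a third have none. (The two counts come from SAP sections written at different times.)

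**Step 3: how much false literacy DIF could impairment produce?** This needs simulation with assumed inputs.
- From the SAP: 8 items with loading .7 (power section); Models 1 to 3 of Box 1; threshold at the 99th percentile of McFadden ΔR² under no DIF (α = .01), taking the smallest value across items, with a floor of .001.
- Assumed: five response categories; no true literacy DIF; among impaired participants 2 of 8 items have half the slope and a location shift of 1 SD; all impaired participants in the low-literacy group unless stated.
- Trait scores were estimated from the items (EAP). An item counts as flagged if any of the three model comparisons exceeds its threshold. The iterative purification in lordif was not reproduced. There were 400 null and 150 scenario replicates.

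Flag rate on the two affected items, with the chance of flagging at least one of them in brackets:

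| Impaired participants | 152 per group | 91 per group |
|---|---|---|
| None | 0.04 (0.07) | 0.05 (0.10) |
| 5% of low group | 0.03 (0.05) | 0.03 (0.05) |
| 10% of low group | 0.04 (0.09) | 0.04 (0.09) |
| 20% of low group | 0.08 (0.15) | 0.10 (0.19) |
| 30% of low group | 0.16 (0.30) | 0.12 (0.25) |
| 20% low, 5% adequate | 0.06 (0.11) | 0.03 (0.05) |
| 20% of both groups | 0.02 (0.05) | 0.06 (0.11) |
| 30% of low group, slope halved only | 0.05 (0.09) | 0.04 (0.09) |
| 20% of low group, location shift only | 0.12 (0.25) | 0.11 (0.18) |

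The rate with none impaired exceeds 1% because three comparisons are made and the smallest threshold across items is used.

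**Step 4: simulation noise.** Treat the two items as independent: 300 item tests per scenario and 800 under the null. At 152 per group:
- 20% impaired: SE = √(0.08 × 0.92 / 300 + 0.04 × 0.96 / 800) = 0.017, so the rise of 0.04 is about 2.3 SE.
- 30% impaired: SE = √(0.16 × 0.84 / 300 + 0.04 × 0.96 / 800) = 0.022, so the rise of 0.12 is about 5.4 SE.

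**Step 5: impairment acting on all items.** With the slope halved on all eight items and shifts of 0 or 0.5 SD, at 91 per group, the mean number of items flagged was 0.23 to 0.32, against 0.30 with none impaired. The common effect is absorbed into the trait score.

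**Step 6: effect of removing flagged participants.** At 20% impaired and 152 per group, the flag rate went from 0.08 to 0.06. The difference of 0.02 is about one SE (√(0.08 × 0.92 / 300 + 0.06 × 0.94 / 300) = 0.021), and the threshold was not recalibrated for the smaller sample. So the simulation does not establish a numerical benefit. If 10% to 20% of the low group were removed, a stratum of 304 would fall to 304 − 15 = 289 or 304 − 30 = 274, and one of 182 to about 173 or 164.

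**The case against.** **The shares that matter may not be plausible.** The protocol says such people *may* be referred, registry access had only been requested, and the routes are described for Northwestern alone. ADRD testing began on 10 July 2019, and one SAP section takes baseline data through March 2020. At the planned 17 per month, 8 × 17 = 136 Northwestern enrolments of every kind. If half of 728 are low-literacy (assumed), that is 364 people, and 30% of them is 109. This argues against 30% overall. It does not settle the matter: another SAP section dates the stop of recruitment to March 2021 (20 × 17 = 340), and referrals could cluster in one stratum.

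**Impaired people can belong to the target population.** The protocol defines health literacy as a capacity to obtain, process and understand health information, and the SAP's study population is broad. Removing them from the primary analysis would change what is estimated, after data collection. This stands, and it is why the full sample should stay primary.

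**The data are not inseparable.** The diagnosis is recorded and everyone is screened with the SPMSQ. This also stands: the gap is in the analysis plan, not in data capture.

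**Stronger readings.** A reader might infer that the literacy DIF results are materially biased. The documents give neither the number of referrals nor their spread across literacy groups, so they do not support that. A reader might also infer that noisier answering by impaired people would by itself produce the predicted lower slopes as flagged DIF. In the simulation, slope loss alone added almost no flags.

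**Conclusion.** The gap is real: a recorded, foreseeable confounder of the literacy contrast appears in none of the literacy analyses in the available SAP text. The MoCA-B split does not close it, because it covers two depression scales and ignores literacy.

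The size is unknown. Under the assumptions above, inflation appeared only when about 20% to 30% of the low-literacy group was impaired, the impaired were confined (or nearly so) to that group, and impairment moved the location of some items but not others. At 5% to 10%, or with impairment balanced across groups, it could not be told from the null rate. This is an unquantified possibility and a cheap improvement to the plan, not a demonstrated bias.

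Separately, the *significant* and *severe* wordings of the exclusion differ, and the SAP's description of its population does not mention the referrals. The passages must be reconciled whatever the size of the effect.

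**What to change.** Keep the full-sample analyses as primary and add to the SAP:

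1. A table of participants with the REDCap impairment flag, by Health LiTT group, language and mode. If the flagged share is small or balanced, this alone largely answers the point.
2. A prespecified repeat of the literacy DIF analyses (lordif and MNLFA) and the depression moderation models without flagged participants, with lordif thresholds recalculated for the reduced sample.
3. A reporting rule: attribute an item's DIF to literacy only if it is similar in both runs. Judge this on ΔR² and item parameters, not on whether the flag persists, because the repeat has fewer participants.

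Date the addition and state what had been analysed by then. The SAP labels analyses that were not pre-registered as post-hoc and exploratory, so without an amendment this check would have only that status.

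Reconcile the impairment exclusion in Protocol 3.0 and the SAP's Data Collection Procedures with Protocol 4.14 and 8.0, and mention the referral routes under Study Populations.

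The cost is one extra run per scale, some SAP text, and slightly less precision in the repeat. The repeat cannot deal with undiagnosed impairment, and the report should say so.

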8.0 Consent Process

Consent will be obtained from the patient by bilingual (English/Spanish) research staff. The informed consent process is expected to take up to 20 minutes. Research coordinators obtaining consent will verbally explain the form and also allow time for the participant to read the form in its entirety. The participant will be free to consult with family if desired. After all the participant's questions have been answered, the research staff will ensure the participant understands the purpose and procedures involved in the study by relying on the Informed Consent and Authorization Toolkit for Minimal Risk Research recommendations. Specifically, research staff will implement the teach-back method and ask participants questions about the consent process. Participants will be given time to make a decision about their enrollment once it is established that they possess an appropriate level of understanding of all aspects of the consent process. Otherwise, they will be screened out. The original signed written consent form will be kept separately from research data and a signed copy will be given to the patient. Spanish speaking participants will have access to translated Spanish translated materials and the Spanish-speaking research coordinators will ensure that they understand all aspects of the verbal and written information given to them during the informed consent process.

The consent process for the phone-based protocol will also be obtained from the participant by bilingual (English/Spanish) research staff. The informed consent process will be done via phone and is expected to take up to 20 minutes. Research coordinators obtaining consent will verbally explain the form over the phone and allow time for the participant to ask questions. After all the participant's questions have

been answered, the participant will be asked if they agree to the consent. If they agree, the research coordinator will mark that they agree in a REDCap consent form and then the research coordinator will e-sign their name, print their name, and date the form. If requested, the research coordinator will email or mail a completed copy of the consent form to the participant.

This research will not be recruiting neonates, prisoners, persons under the age of 18, or adults with severe cognitive impairment. Pregnant women will be eligible to participate with their informed consent. This study involves only the completion of self-report questionnaires. Thus, we do not foresee any risks to pregnant women or to the pregnancy. All participants will be screened for cognitive impairment by the research coordinator using the SPMSQ to determine eligibility for this study. Only those deemed capable of providing consent (based on the SPMSQ score) will be considered for the study and their diagnosis of mild-to-moderate cognitive impairment will be noted in the study's REDCap project. Any participant deemed to have severe impairment on this screening test will be deemed ineligible to participate.

8.1 Waiver of Participant Signature on Consent Form (for phone-based protocol)

The phone-based protocol will be conducted entirely remotely by phone. For this reason, we will not be requiring a signature from the participant on the consent form for this protocol. For this portion of the study, we plan to verbally consent participants utilizing a REDCap e-consent form. Instead, we will verbally consent the participant over the phone by reading the consent information to them and asking them a few consent comprehension questions. After thorough explanation, the research coordinator will ask the participant if they verbally consent. If they agree, the research coordinator will mark that they agree in a REDCap consent form and then the research coordinator will e-sign their name, print their name, and date the form. If requested, the research coordinator will email or mail a completed copy of the consent form to the participant.

9.0 Process to Document Consent:

We will be following "SOP: Written Documentation of Consent (HRP-091)."

10.0 Risks to Participants:

This study is low risk; only standard questionnaires and interviews are being used, none of which have significant risks beyond any discomfort associated with answering health questions. Some participants may experience some emotional distress when answering sensitive questions. Our team, however, has a high level of clinical experience and will be able to discuss these issues with participants as needed, and provide appropriate referrals if desired by a participant.

11.0 Adequacy of Protection against Risks:

All research proposals are submitted for approval to the Northwestern University Institutional Review Board and the Boston University Medical Campus (BUMC) Institutional Review Board. All research personnel are trained and certified in research and HIPAA regulations. Established policies and procedures allow for all individuals receiving healthcare at Northwestern Medicine and Boston Medical Center and affiliated Community Health Centers to be considered as potential candidates for research, with study personnel only approaching eligible patients after they have been informed of the study's nature by their healthcare provider, and agree to be approached.

Participants will be withdrawn at their request. If a participant wishes to withdraw, we will document the reasons for withdrawal for tracking purposes and for reporting to the IRB.

12.0 Financial Compensation:

In-person protocol: Participants will receive \$40 upon completion of the baseline visit, \$50 after the 3-month visit, and \$60 after the 6-month visit in the form of cash. In addition, they will receive parking passes at each one of their visits to cover the cost of their parking if they parked in a specified Northwestern garage. If needed, taxi transportation will be arranged for participants, which will be paid for by the research project. Participants will receive up to \$22.50 for transportation costs. Participants will also be compensated \$25 upon completion of the cognitive screening questions.

Phone-based protocol: Participants will receive \$40 upon completion of the baseline visit, \$50 upon completion of the 3-month follow-up, and \$60 upon completion of the 6-month follow-up. Payment will be made in the form of gift cards (either physical gift card or e-gift card, depending on participant preference).

12.1 Participants may be liable for covering transportation costs if those exceed \$22.50. Further, they may be billed for research-related injuries. Specifically, all medical care will be billed to the participant, their insurance, or another third party. Northwestern Medicine has no program to pay for medical care for research-related injury. It is very unlikely that this study will cause any injuries; the study involves only completing standard questionnaires. If at any moment a participant refuses to answer a questions or withdraws from the study, they will still be compensated for that particular study visit.

13.0 Provisions to Protect the Privacy Interests of Participants:

Data on social and medical history (e.g., age, date of birth, gender, and race/ethnicity) will be obtained from the patient's electronic medical record to maintain privacy. Medical history data will be extracted from Epic via the EDW for purposes of calculating a single index of medical comorbidity, the Charlson Comorbidity Index. This index uses the presence versus absence of administrative codes in the medical record to determine certain diseases and syndromes that may be present; these include myocardial infarction, congestive heart failure, peripheral vascular disease or bypass, cerebrovascular disease or transient ischemic disease, hemiplegia, pulmonary disease/asthma, diabetes, diabetes with end organ damage, renal disease, mild liver disease, severe liver disease, gastric or peptic ulcer, cancer (lymphoma, leukemia, solid tumor), metastatic solid tumor, dementia or Alzheimer's disease, rheumatic or connective tissue disease, HIV or AIDS, hypertension, skin ulcers/cellulitis, depression, and warfarin use. These data will be combined into a single number that summarizes the degree of comorbidity faced by the individual patient. Data will be analyzed to determine whether health literacy and medical comorbidity interact in determining responses to questionnaires.

Other than the above-mentioned medical history and demographic variables, no other data will be retrieved from Epic.

Participants will interact with the study coordinator who will verify age, date of birth, race, and ethnicity date. The study coordinator will be the point person to answer any and all questions about the study. All study procedures will be conducted in a private space. Participants will be informed that they are allowed to skip any question that makes them feel uncomfortable or that they would not like to answer. Participants will be made aware of all of the examinations and research procedures that will take place ahead of time so that they are fully aware of what is required of them. The subject will be able to withdraw from the research study at any time. The research team is permitted to access the participants' medical records, which includes social and medical history. Only information that is pertinent to the research study will be viewed and collected. Any information that will be put into our databases will be collected from the EDW.

14.0 Confidentiality and Data Management:

Special procedures for ensuring patient confidentiality will be implemented. Data transmission and the distributed data systems will have multiple layers of security. All study data will be entered into the electronic data entry system by study coordinators at Northwestern. All databases will be on password protected computers, and the database will be password protected. The database will be stored on a Northwestern share drive, which is regularly backed up. Paper data (i.e. consent forms, data collection forms) collected from participants will be stored in a locked file cabinet at [name], in the department of Medical Social Sciences. Only authorized research personnel will have access to this data.

Each study subject will be assigned an identification number. Only this number will be used to identify subjects in any individual tabulation. The PHI that is collected will represent the minimum necessary to successfully execute the study.

Any PHI will be securely requested via the EDW. Only group-level data will be included in publications and presentations. If individual participated data are to be published, no identifying information will be included. The study files will be maintained in a secure location in our department. Access to computerized data will be restricted to study personnel. Password authorization will be enforced. Previous use of this security system and a secured server indicates that this technique is very successful in assuring the protection of confidential information.

The data will be stored on a secure server with restricted access. Nonetheless, there is always the possibility of unauthorized release of data about the participants. Such disclosure would be extremely unlikely to involve a threat to life, health, or safety. It is conceivable that such disclosure could have psychological, social, or legal effects on the patient. Using the standard security procedures (described above) can effectively minimize the risk of unauthorized disclosure of data. All study personnel who have access to patient data will be educated regarding the need to protect confidentiality and the procedures to be followed to ensure such protection. After the study is completed, the databases will be stored on public repositories. The databases in these repositories will be de-identified to obviate further privacy and security considerations.

Authorized representatives of the National Institutes of Health (NIH), as well as authorized members of the IRBs, will have also have access to study records.

There are no specimens associated with this study.

15.0 Data Monitoring Plan to Ensure the Safety of Participants:

We are asking questions about depression and anxiety, for which good treatments exists. As such, we will give all participants a referral list for possible mental health treatment, with information letting them know that they can contact us at any time for additional help finding a referral. Giving this information to all participants ensures that no person will be missed, and also reduces any feelings of stigma that might arise if the person felt singled out based on their responses. As described above, we will monitor the suicidality item of the PHQ-9 at each and every visit. Based on the PHQ-9, the coordinator will follow up as needed with the C-SSRS to assess whether additional assessment and/or intervention are needed. The C-SSRS will serve as the report form to document this additional information. For any participant with moderate or greater risk, a licensed psychologist or physician on the research team will talk to the participant to gather more information and make appropriate recommendations and referrals. As described above, any immediate suicidal intent will be treated as a life threatening emergency. We will take the person to the Emergency Department or involve emergency services from 911 if needed.

16.0 Data and if applicable, Specimen Banking:

No Biosample Storage and Shipment will be used

17.0 Qualifications to Conduct Research and Resources Available:

Our team includes the PI, a licensed clinical psychologist with extensive experience delivering psychotherapy as well as in health-related research. We also have licensed internists on the team. Our team has extensive experience working with patients across a variety of settings. Additionally, our research coordinators have graduate degrees and extensive experience interpreting and translating documents from English to Spanish.

No additional psychological or medical resources should be needed as a result of this study. If further needs should arise, however, the study PI will assist the participant in getting connected with appropriate follow-up care. All participants will be given a referral list at the end of the study.

References

